13.4 Sample Size Considerations

We calculated power for comparing the primary endpoint within matched cluster pairs, *survival with suppressed viral load, defined as HIV RNA <150 copies/mL in plasma or serum, at 24 months*, among the cohorts of HIV-positive study participants. Cluster-randomized designs require consideration of the between-cluster coefficient of variation (k), a measure of variation between clusters. In general, the more variability in outcome between clusters, the larger the sample size required to detect a given difference. The coefficient of variation in a matched study needs to take into account the matching correlation (k_m), in other words how much of a reduction in pair variability is accomplished by matching. More successful matching is associated with lower k_m values. We calculated the k_m using baseline RDS data from a prior trial for a hypothetical set of matched pairs based on the proposed matching criteria for this trial as described above. The values of k_m ranged from 0.08 to 0.15 when considering RDS-II weighted and unweighted estimates of the outcome of interest. In addition to consideration of k_m , we also considered other factors specified by the sample size formula from Hayes et al. (6):

$$c = 2 + (Z_{\alpha/2} + Z_{\beta})^2 [\pi_0(1 - \pi_0)/n + \pi_1(1 - \pi_1)/n + k_m^2(\pi_0^2 + \pi_1^2)](\pi_0 - \pi_1)^2$$

where π_0 and π_1 are the true population proportions in the absence and presence of the intervention, respectively, n is the number of individuals within each cluster, $Z_{\alpha/2}$ and Z_{β} are the standard normal distribution values corresponding to the upper tail probabilities of $\alpha/2$ and β , respectively and k_m is the coefficient of variation within matched pairs.

Within our calculations, we varied the k_m from 0.10-0.20 based on our preliminary data, the sample size per cluster from 50-150 to account for varying levels of loss to follow-up, and the outcome prevalence in control condition clusters from 25-45%. The number of cluster pairs needed was relatively insensitive to the prevalence of outcome in the control group and the cluster size as long as the sample size was >70 per cluster.

Figure 2 shows the number of cluster pairs needed (y-axis) to provide 80% power to detect differences of 0.05 to 0.30 (x-axis) across a range of k_m values (different colored lines) assuming a sample size of 150 per cluster, two-sided alpha=0.05, and 25% outcome prevalence in the

control clusters. With 8 cluster pairs, we will have 80% power to detect differences of 8 percentage points (risk ratio = 1.32) if the k_m is 0.10, and 10 percentage points (risk ratio = 1.4) if the k_m is 0.15. If the prevalence in control clusters is 40% then the detectable difference is 10 percentage points (risk ratio = 1.4) if the k_m is 0.10.

[figure not shown]

Figure 2. Number of matched pairs needed to detect differences. Red dotted line indicates 8 pairs of clusters

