8.3 Participant Retention

Once a participant enrolls in the cohort study, the study site will make every effort to retain

him/her for the full study period (24 months), to minimize possible bias associated with loss-to-follow-up. Retention rates of 80% at 24 months are targeted among non-deceased participants. Study site staff are responsible for developing and implementing local standard operating procedures to target this goal. Components of such procedures include:

- Thorough explanation of the study visit schedule and procedural requirements during the informed consent process and re-emphasis at each study visit.
- Collection of detailed locator information at the baseline visit, and active review and updating of this information at each subsequent visit.
- Use of mapping techniques to establish the location of participant residences and other locator venues.
- Use of appropriate and timely visit reminder mechanisms to retain participants.
- Immediate and multifaceted follow-up on missed visits.
- Mobilization of trained outreach workers or “tracers” to complete in-person contact with participants at their homes and/or other community locations.
- Regular communication with the study community at large to increase awareness about HIV/AIDS and explain the purpose of HIV treatment research and the importance of completing research study visits.

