Protocol revisions due to COVID-19: Cohort study participant enrollment was completed in October, 2018. Study activities (follow-up visits and incentive intervention) were suspended indefinitely in March 2020. At the time research activities were suspended, all participant visit windows had closed for the 6- and 12-month follow-up visits. However, 65 and 959 participants had not completed the 18- and 24-month visits, respectively, but had not reached or were within the visit window. Because of this, in Protocol Version 2.0 we revised the primary endpoint from 24 months to 12 months. Data that was collected at 18 and 24 months will be considered in secondary and sensitivity analyses.

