13.2.1 Primary Endpoint

Survival with suppressed viral load, defined as HIV RNA <150 copies/mL in plasma or serum, at 12 months.

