13.9.1 Analysis plan for primary outcome

In the primary analysis, we will use an intent-to-treat, missing equals failure approach. The primary outcome will be the proportion of participants who have survived with a suppressed viral load (HIV RNA <150 c/mL) at the 12-month cohort follow-up visit. Participants that die prior to the 12-month visit or miss the 12-month visit will be considered failures in the analysis. The primary analysis will be at the site-level and will use a two-stage procedure beginning with fitting an individual-level logistic regression model with terms for each matched pair and individual-level viral suppression at the baseline visit (HIV RNA <150 copies/mL), but ignoring the intervention effect. The model computes the expected number of events in each cluster. The observed and expected number of events in the two clusters in each matched pair are compared and if there is no intervention effect these values will be the same. An adjusted prevalence ratio and 95% confidence interval will be calculated by estimating the mean within-pair difference of the natural log transformed adjusted prevalences by arm. The exponentiated difference is the ratio and a paired t-test will be used for significance testing. An adjusted prevalence difference and 95% confidence interval will be calculated in a similar manner, estimating the mean within pair difference of the non-transformed prevalences by arm. Analysis of the primary outcome will also be stratified by viral suppression status at baseline (HIV RNA <150 copies/mL). In this site-level one-stage approach, we will calculate the difference in the proportion with suppressed viral load within each matched pair among strata defined by baseline viral suppression. We will calculate the unweighted mean of the pair-wise difference with a 95% confidence interval and use a paired t-test to test the hypothesis that within each stratum the observed difference is statistically different from zero. We will further explore whether there is statistically significant interaction by baseline viral suppression status and intervention effect.

Primary outcome sensitivity analyses

We will conduct several supplemental analyses to assess whether inferences are sensitive to different analytic specifications. First, we will conduct an analysis in which participants who

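### Section 13.4 prints a risk ratio of 1.4 for 40% versus 50% (it is 1.25), and its claim that the pairs needed barely depend on control prevalence and cluster size fails at the 8 to 10 points it says it can detect

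*Combined protocol and SAP*

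**What the plan says.** Section 13.4 works with 8 matched pairs, 150 participants per cluster, two-sided alpha 0.05 and 80% power. It states three detectable differences:

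- 25% control, k_m 0.10: 8 points, risk ratio 1.32.
- 25% control, k_m 0.15: 10 points, risk ratio 1.4.
- 40% control, k_m 0.10: "prevalence in control clusters is 40% then the detectable difference is 10 percentage points (risk ratio = 1.4".

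The section reports having varied k_m over 0.10 to 0.20, control prevalence over 25% to 45%, and "the sample size per cluster from 50-150 to account for varying levels of loss to follow-up". It describes the number of pairs as "relatively insensitive to the prevalence of outcome in the control group and the cluster size as long as the sample size was >70 per cluster", and names no effect size for that statement. Its own estimates of k_m from earlier survey data run from 0.08 to 0.15.

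The endpoint used in the calculation, described there as primary, is "survival with suppressed viral load, defined as HIV RNA <150 copies/mL in plasma or serum, at 24 months". Section 13.1 records that "in Protocol Version 2.0 we revised the primary endpoint from 24 months to 12 months", and section 13.2.1 now defines the primary endpoint as "Survival with suppressed viral load, defined as HIV RNA <150 copies/mL in plasma or serum, at 12 months". Section 13.2.2 lists 24 months as secondary.

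**The concern.** The third ratio cannot be right: 10 points above 40% is 50%, and 1.4 is the ratio for the case just before it, 25% versus 35%. The primary analysis in section 13.9.1 reports a prevalence ratio as well as a prevalence difference, so an error in one of only three stated detectable ratios misinforms the reader on a reported scale.

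The sentence on insensitivity matters more for interpretation. No figure is given for 40% control at k_m 0.15, the upper end of the plan's own estimates. A reader who trusts the sentence would carry the 10 points stated for 25% control over to a higher control prevalence and believe that 8 pairs still give 80% power.

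The power statement is also attached to an endpoint that is no longer primary, and nothing is stated for the one that replaced it.

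**Working it through.** **Inputs (section 13.4).** Two-sided alpha 0.05, 80% power, n = 150 per cluster, 8 pairs, k_m 0.10 to 0.20, control prevalence 25% to 45%. Section 8.3 supplies an illustrative smaller n: "Retention rates of 80% at 24 months are targeted among non-deceased participants", and 0.80 × 150 = 120.

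**Formula.** With π0 the control and π1 the intervention proportion,

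c = 2 + (1.960 + 0.842)² × [π0(1−π0)/n + π1(1−π1)/n + k_m²(π0² + π1²)] / (π0 − π1)²,

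where the squared sum of normal quantiles is 7.849. In the text as read from PDF, no division sign stands before the last factor. It is read as a divisor, because the stated cases reproduce only that way.

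**Step 1: reproduce the plan's three cases.**

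- 25% vs 33%, k_m 0.10: 2 + 7.849 × (0.001250 + 0.001474 + 0.001714)/0.0064 = 7.44, so 8 pairs.
- 25% vs 35%, k_m 0.15: 2 + 7.849 × (0.001250 + 0.001517 + 0.004163)/0.01 = 7.44, so 8 pairs.
- 40% vs 50%, k_m 0.10: 2 + 7.849 × (0.001600 + 0.001667 + 0.004100)/0.01 = 7.78, so 8 pairs.

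All three differences reproduce.

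**Step 2: the ratios.** 0.33/0.25 = 1.32 and 0.35/0.25 = 1.40 agree with the text. 0.50/0.40 = 1.25 does not. Other readings do not give 1.4 either: the odds ratio is (0.50/0.50)/(0.40/0.60) = 1.5, and a fall from 40% to 30% gives 0.40/0.30 = 1.33. A ratio of 1.4 at 40% control would mean 56%, a 16-point difference, for which c = 4.45 (5 pairs).

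**Step 3: control prevalence, n = 150.** Power is for 8 pairs by the paired t-test: noncentral t, 7 df, noncentrality (π1 − π0)/√(bracket/8).

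| Difference, k_m | | 25% control | 40% control | 45% control |
|---|---|---|---|---|
| 8 points, 0.10 | pairs needed | 7.4 | 10.8 | 12.0 |
| | power | 83% | 63% | 58% |
| 10 points, 0.15 | pairs needed | 7.4 | 11.8 | 13.5 |
| | power | 83% | 59% | 52% |
| 10 points, 0.10 | pairs needed | 5.6 | 7.8 | 8.6 |
| | power | 94% | 81% | 76% |

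For example, 40% vs 50% at k_m 0.15: 2 + 7.849 × (0.001600 + 0.001667 + 0.009225)/0.01 = 11.80.

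**Step 4: cluster size, 25% vs 33%, k_m 0.10.** Pairs needed are 7.4 at n = 150, 8.3 at n = 120 (power 77%) and 11.2 at n = 71 (power 61%), although 71 is above the stated threshold of 70.

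**Step 5: where the sentence does hold.** At 20 points and k_m 0.10, c is 3.09 at 25% control and 3.85 at 45%. If the ratio is held fixed instead of the difference, pairs needed fall as prevalence rises: at ratio 1.32 and k_m 0.10, 7.4 at 25% (33%) and 5.3 at 45% (59.4%).

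**Step 6: endpoint.** Section 13.4 names 24 months and sections 13.1 and 13.2.1 name 12 months. No section gives a 12-month control prevalence or a 12-month detectable difference.

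**The case against.** The ratio is a slip in one number, and nothing else in the plan uses it. That is fair, but it is still wrong as printed.

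The sentence on insensitivity is qualitative, and the calculations covered differences of 0.05 to 0.30, over much of which it is roughly true. The section also shows some dependence itself, since 8 points becomes 10 at 40% control. Both observations are correct. But the section's claims are for 8 to 10 points, and its own 40% figure contradicts the sentence rather than qualifying it, for k_m 0.10 only.

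The strongest point is that the steep figures come from holding k_m constant, so that the between-cluster standard deviation grows with prevalence. With the standard deviations kept at their values for 25% control, 10 points (k_m 0.15) needs 7.4, 7.8 and 7.9 pairs at 25%, 40% and 45% control, and 8 points (k_m 0.10) needs 7.4, 8.1 and 8.2. That would nearly rescue the sentence. It is not the plan's model, however: the formula takes k_m as the parameter, and the stated 10 points at 40% follows from constant k_m. Under constant standard deviations it would be just over 8 points.

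At k_m 0.08, the low end of the estimates, 10 points needs 5.1, 6.6 and 7.1 pairs, so 8 pairs suffice. But 0.08 lies outside the range the plan says it varied, and 8 points still needs 9.1 and 9.9 pairs at 40% and 45%.

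Two limits stand. Smaller n does not reach the primary analysis through loss to follow-up, because participants who "miss the 12-month visit will be considered failures in the analysis". The formula also ignores the planned adjustment for baseline suppression, so its results are not exactly those of the planned analysis. On the endpoint, the change to 12 months is openly explained and the formula has no time term. That makes this part a matter of labelling and a missing statement.

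**Conclusion.** The concern holds. The risk ratio for 40% versus 50% is 1.25, not 1.4; the 10 points and 8 pairs are correct. The statement of insensitivity does not hold at the differences the section claims: across 25% to 45% control, the requirement rises from 7.4 to 12.0 pairs (8 points, k_m 0.10) or from 7.4 to 13.5 pairs (10 points, k_m 0.15), and power with 8 pairs falls from 83% to 58% or 52%. The milder case, 10 points at k_m 0.10, falls only to 76%.

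These figures rest on the section's own formula with k_m held constant, a fixed absolute difference (the scale of Figure 2 as described) and n = 150. They do not show that the design is inadequate: the three stated differences stand, and no loss of power at 12 months is asserted. The absence of a 12-month statement is real but secondary, and the conclusion does not depend on it.

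**What to change.** 1. In section 13.4, change the risk ratio for the 40% case from 1.4 to 1.25.
2. Replace the sentence on insensitivity with the detectable differences for 8 pairs, n = 150 and 80% power (the formula solved for c = 8), stating that k_m is held constant across control prevalence:

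| Control prevalence | k_m 0.10 | k_m 0.15 | k_m 0.20 |
|---|---|---|---|
| 25% | 7.6 points | 9.5 points | 11.8 points |
| 40% | 9.8 points | 13.1 points | 17.2 points |
| 45% | 10.5 points | 14.3 points | 19.0 points |

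3. Say that a smaller n applies to low enrolment or to the sensitivity analyses that exclude missing participants, not to the missing-equals-failure primary analysis through loss to follow-up.
4. Keep the existing calculation, labelled as done for the former 24-month primary endpoint, now secondary. Add a detectable-difference statement for the 12-month primary endpoint, giving the control prevalence assumed under missing equals failure.

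The cost is a few lines and one table. Design, enrolment and analysis are unchanged. The stated power becomes less favourable where control prevalence exceeds 25%.

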13.5 Study Site Selection and Pair Matching

Study sites (cities) are the units of randomization in the current trial. In a prior cluster randomized trial that concluded in June 2017, we evaluated the effectiveness of ICCs for increasing rates of HIV testing among PWID and MSM in 22 sites across India (ClinicalTrials.gov identifier: NA00047702) (1, 2). From the sites in the prior trial, we selected 16 well-characterized sites for the current trial. The site selection criteria included 1) large estimated number of HIV-positive key population members (PWID or MSM depending on the site), 2) poor HIV care continuum indicators (low awareness of HIV status, low linkage to care and ART, and low prevalence of viral suppression), and 3) ability to match the site with another site (see below).

Close matching of characteristics of interest in matched pairs can increase the efficiency of cluster randomized trials (6). To match sites, we considered data from RDS surveys of PWID or MSM conducted in 2012/2013 and again in 2016/2017 (n~1000 participants per site), but also drew from our research team's prolonged experience at the sites. Absolute matching criteria included the key population (PWID sites could only be paired with PWID sites and MSM sites could only be paired with MSM sites) and whether or not the site was an intervention site (ICC) or usual care site in the prior trial - former intervention sites already had ICCs up and running, but new ICCs needed to be launched in former usual care sites (former intervention sites were

paired only with other former intervention sites and former usual care sites were paired only with former usual care sites). These strata resulted in the categorization shown in Figure 3.

Figure 3. Stratification of sites for pair matching

		Treatment condition in trial ending 2017	
		Former ICC site	Former usual care site
Key population	PWID	
 • Aizawl • Bilaspur • Dimapur • Ludhiana 	
 • Amritsar • Churachandpur • Delhi • Kanpur
	MSM	
 • Bangalore • Belgaum • Hyderabad • Visakhapatnam 	
 • Bhopal • Delhi • Madurai • Vijayawada

Within the above stratification, we considered PWID/MSM population size, geography, and HIV-related community characteristics - HIV prevalence, viral suppression, and prevalence of viremia - when evaluating potential pair matches. Final criteria that were considered in the matching process in order of prioritization were: 1) proportion of HIV-positive persons with viral suppression; 2) HIV prevalence; and 3) prevalence of viremic persons, 4) estimated size of the target population. Final pair matching is listed in Figure 4:

Figure 4. Site pairs, by key population	
PWID	MSM
Pair 1: Aizawl and Bilaspur	Pair 1: Bangalore and Visakhapatnam
Pair 2: Churachandpur and Amritsar	Pair 2: Belgaum and Hyderabad
Pair 3: New Delhi and Kanpur	Pair 3: Bhopal and Vijayawada
Pair 4: Dimapur and Ludhiana	Pair 4: Madurai and New Delhi

13.6 Randomization and Masking Procedures

In cluster-randomized trials with a relatively low number of sites (clusters), substantial imbalances between study arms can emerge easily by chance. To reduce the likelihood of large study arm imbalances for key variables, we restricted the pool of potential allocation combinations by removing combinations with large baseline imbalances. With no restrictions, there were a total of 16 potential allocations (i.e., 4^2) within each stratum (PWID/MSM), or 256 overall allocations. First, to reduce large imbalances within the strata, randomization allocations were dropped ($n=8$, 4 in each stratum) due to imbalances in prevalence of viremic persons or viral suppression (i.e., all sites with higher/lower prevalence were allocated to one arm). This resulted in 12 allocations for each stratum. These allocations crossed (PWID x MSM), resulted in 144 potential allocations (i.e., 12^2). Then, an additional overall restriction was placed in which allocations were dropped ($n=36$) due to imbalances in prevalence of viremic persons or viral suppression (i.e., higher/lower prevalence 6:2 pair ratio in different arms). This resulted in a total of 108 potential allocations. We checked across all these potential allocations for sites that either always or never appeared in the same study arm. No sites always or never appeared in the same

arm - with the exception matched sites, which, by definition, never appeared in the same arm.

Of the 108 allocation combinations that remained after site pairing and restriction, one allocation was selected in a ball drawing ceremony on January 3, 2018 that was refereed by two statisticians who were independent of the study. The ceremony was video recorded and is available at <https://youtu.be/UmXBG2CluNA>. Because of the cluster randomized design, masking participants or research staff was not feasible. However, the randomization team withheld the randomization results for each site pair until cohort recruitment was complete or nearly complete at both sites in the pair. The implementation teams in India recruited cohorts at each site without knowing whether the site would be intervention or control.

13.7 Participant Enrollment and Follow-up

Cohort participants will be assessed for eligibility and enrolled at ICCs as described above. These participants will complete a baseline study visit as soon as possible after screening and will be asked to complete follow-up research visits at 6, 12, 18, and 24 months. Participants in the qualitative evaluations will be enrolled at ICCs and be asked to complete an in-depth interview. There will be no follow-up visits in the qualitative evaluation. Participants in the RDS survey will be enrolled after being recruited by network members using a coupon system as described above. RDS survey participants will be asked to complete a single study visit with no follow-up.

13.8 Data and Safety Monitoring

Procedures to ensure the validity and integrity of the data

All field staff, interviewers, phlebotomists and clinicians who will come into contact with study participants will be required to complete research ethics and good clinical practice (GCP) training. All staff will undergo a three-day training program on the study protocol and the standard operating procedures, followed by a one-day one-on-one training session for staff who will be administering and/or recording information on tablet PCs/netbooks (RDS) or study case-report forms (ICCs). Mock interviews will also be included. If new staff members are hired during the course of the trial, they will undergo similar training prior to coming into contact with study participants.

Lab technicians/phlebotomists at YRG CARE have undergone training on research ethics and good clinical laboratory practices (GCLP). The YRG CARE ID Lab is certified by the College of American Pathologists, United Kingdom National External Quality Assurance Scheme, and the Virologic Quality Assessment Program, US and by the AIDS Clinical Trial Group and Abbott Laboratories Inc, US. GCLP are monitored by Johns Hopkins, Family Health International, and PPD.

Procedures to guarantee the accuracy and completeness of the data

Our primary mode of data collection will be through the cohort and RDS surveys. In addition, some process measure data will be collected in the ICCs. We have chosen to use a laptop data entry system rather than paper case report forms. Given the large number of surveys/study visits that will be conducted (16,000 in RDS and ~8,000 in cohort), the electronic data collection method has advantages over the paper method, including 1) immediate data upload to the central

server, 2) increased portability for multiple sites, 3) reduced need to transport paper forms, and 4) logic checks and field restrictions can be built into the program to minimize data capture errors. Finally, the ability to upload data from the field to a central server in real time will help us identify potential overlap between sites (i.e., participants who are recruited at more than one site). The central database will include the unique alphanumeric codes that will be obtained from fingerprint images. Therefore, once a survey is completed the code will be centrally available, enabling us to quickly identify individuals recruited at multiple sites.

